**Randomized Clinical Trial Evaluating the Efficiency and
Safety of Holmium Laser with Moses Technology versus
SuperPulsed Laser System with Thulium Laser on Renal
and Ureteral Stones**

Principal Investigator: [name]
Co-Investigator: [name]; [name]; [name]
Affiliation: University of Wisconsin-Madison, School of Medicine and Public Health,
Department of Urology

NCT04963062
Protocol 2021-0695

PROTOCOL TITLE:

Randomized Clinical Trial Evaluating the Efficiency and Safety of Holmium Laser with Moses Technology versus SuperPulsed Laser System with Thulium Laser on Renal and Ureteral Stones

LEAD RESEARCHER:

PI: [name] [contact]

Co-Investigators

[name], [contact]

[name]; [contact]

[name], [contact]

[name]: [contact]

[name]: [contact]

VERSION NUMBER/DATE:

Version 3, 8/30/2021

REVISION HISTORY

Revision #	Version Date	Summary of Changes	Consent Change?
1	6/14/2021	Initial IRB review modification requests	Yes
2	7/22/2021	Change of protocol	No
3	8/30/2021	Change of protocol	No

Project Summary

This is a prospective randomized controlled trial designed to assess the efficiency of Lumenis® Pulse™ P120H holmium laser system with the Moses technology (holmium laser with Moses) versus the Soltive™ SuperPulsed Laser System with the thulium fiber laser technology (thulium laser), in fragmentation of upper tract urinary stones during ureteroscopy with laser lithotripsy. Specifically, we will compare procedural time, intra-operative parameters and stone free rates. Laser lithotripsy is a surgical procedure performed during stone surgeries. Both lasers are FDA approved and clinically used in the United States. Currently, at University of Wisconsin, we are using the holmium laser with Moses during ureteroscopies and we will soon have the thulium laser for clinical use as well. At our institution, we perform approximately 200 outpatient ureteroscopies with laser lithotripsy annually. Typically, we have evaluated surgical outcomes as part of routine quality improvement initiatives or as IRB-approved retrospective reviews. However, in this scenario, a randomized trial requiring IRB approval, we have the ability to conduct a higher-level study protocol and rigorously compare the time required for acceptable stone fragmentation using the two different lasers. A randomized trial, unlike a retrospective review of our surgical procedures, will reduce bias sufficiently to allow us to be sure of our results.

Number of Study Sites

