The secondary objective is to compare the primary and secondary outcomes when stratified by stone size. This will allow us to explore the efficiency between Moses and thulium laser on treating large vs. small stones. Previous literature suggested that stone size was associated with operative time.^{ix} Patients will be separated based on the size of their stones: 3-10 mm or 11-20 mm and then randomized to holmium laser with Moses or thulium laser. Patients will be randomized into the groups by a ratio of 1:1.

Research Design and Methods

This study will be a randomized trial comparing ureteroscopy with laser lithotripsy with the Lumenis® Pulse™ P120H holmium laser system with the Moses technology (holmium laser with moses) versus the Soltive™ SuperPulsed Laser System with the thulium fiber laser technology (thulium laser). The primary objective is to compare the procedural time (minutes). We will keep strict timing from the minute the ureteroscope is inserted into the patient to the time the ureteroscope has been removed. The following information will be collected as secondary outcomes: (1) stone free rate; (2) total operative time (minutes); (3) fragmentation/dusting time (minutes, total time to fragment the stone, including the laser was in use and time of pedal pauses); (4) lasing time (minutes, time the laser was in use, not including pedal pauses); (5) total energy used (kilojoules, kJ); (6) laser efficiency (mm per minute); (7) number of times the laser pedals are pressed (left, right, and total pedal presses); (8) stone analysis; (9) complications; (10) quality of life survey (WISQOL short form) both pre-operatively and post-operatively and (11) physician evaluation of the laser. Physicians will complete a one page survey at the end of the case evaluating the laser (survey included as attachment). A total of 3 clinic visits (i.e., pre-operative visit, the stone surgery, and one post-operative visit) will be needed for this study. Stone parameters (i.e. size, location, Hounsfield units, presence of hydronephrosis, stone volume), demographic information, co-morbidities, and post-operative parameters will be collected from the medical record.

Number of Participants

NCT04963062
Protocol 2021-0695

Approximately 164 patients will be enrolled (see Data Analysis for sample size justification).

Inclusion Criteria

1. Patients at least 18 years of age, and less than 89 years old.

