Since we have 5 surgeons participating in this study, we will use university-based cloud service (such as OneDrive) to temporarily save the enrollment log. Study team member will use their Net ID to access the enrollment log. The enrollment log is completely deidentified. Only participant ID (such as 101, 102) and the laser each participant is randomized to are saved in the enrollment log. Once we complete data collection, we will permanently delete it from the cloud.

Share of results

NCT04963062
Protocol 2021-0695

Some of the information collected for this study will go in the patient's medical record. This includes the results of the one-month post-operative image, stone analysis, stone surgery, and all clinic visits information as these are being conducted as standard of care. All other information from research specific procedures will NOT go in the patient's medical records.

We only publish aggregated results. No individual results will be shared. We will not share the data with outside institutions.

Economic burden to participants

This study does not place financial burden to patients. The study interventions are our routine clinical practice to treat stones. It will be same as they are not involved in this study.

The cost of the two laser treatments are equivalent.

Data Analysis

The data collected will be analyzed as an intention-to-treat analysis. Statistical analyses will include T-test and, if appropriate, Chi-square tests (e.g., for categorical data), and two-way MANOVA. Patient demographics and stone characteristics will be summarized as appropriate as continuous variables (mean and standard deviation) or categorical variables (frequency, percentage). To compare the two groups, continuous variables such as procedural time, total OR time, WISQOL etc., will be analyzed using T test and two-way MANCOVA (stratified by stone size 3 - 10 mm or 11-20 mm). The surgeon will be controlled as a covariate. Categorical variables such as stone free rate will be analyzed using chi-square.

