We plan to enroll 164 patients in this study. Patients will be stratified into two groups according to their stone size (3-10 mm or 11-20 mm) and then randomized to either holmium laser with Moses or thulium laser. The stone size is defined as the largest stone size (largest diameter on pre-operative CT), if patients have multiple stones. Previous literature suggested stone size is associated with operative time.^{ix} A significance level of 0.05 will be used with a two-sided two-sample equal-variance t-test. Group sample sizes of 33 and 33 achieve 80% power to detect a significant difference between the means when the mean difference is 4.6 minutes with a standard deviation of 6.5 minutes. We also decide to increase the sample size by 25% (41 patients per group). This will allow for the possibility that the randomization scheme is intra-operatively abandoned for some reason (e.g., equipment failure), that the planned procedure was unable to be completed for some reason, as determined by the surgeon in

charge of the case, and/or that the patient – after his/her procedure – wishes to withdraw from the study and exclude his/her information from our analysis.

ⁱ Scales CD Jr, Smith AC, Hanley JM, Saigal CS; Urologic Diseases in America Project. Prevalence of kidney stones in the United States. *Eur Urol*. 2012 Jul;62(1):160-5.

ⁱⁱ Geraghty RM, Jones P, Somani BK. Worldwide Trends of Urinary Stone Disease Treatment Over the Last Two Decades: A Systematic Review. *J Endourol* 2017 Jun;31(6):547-556.

ⁱⁱⁱ Assimos D, Krambeck A, Miller NL, et al: Surgical Management of Stones: American Urological Association/Endourological Society Guideline, PART II. *J. Urol.* 2016.

^{iv} Andreeva V, Vinarov A, Yaroslavsky I, et al. Preclinical comparison of superpulse thulium fiber laser and a holmium:YAG laser for lithotripsy. *World J Urol*. 2020 Feb;38(2):497-503.

^v Ventimiglia E, Doizi S, Kovalenko A, et al. Effect of temporal pulse shape on urinary stone phantom retropulsion rate and ablation efficiency using holmium:YAG and super-pulse thulium fibre lasers. *BJU Int*. 2020 Jul;126(1):159-167.

^{vi} Bagrodia A, Gupta A, Raman JD, et al. Predictors of cost and clinical outcomes of percutaneous nephrolithotomy. *J Urol*. 2009 Aug;182(2):586-90.

^{vii} Schuster TG, Hollenbeck BK, Faerber GJ, Wolf JS Jr. Complications of ureteroscopy: analysis of predictive factors. *J Urol*. 2001 Aug;166(2):538-40.

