### **Data Analysis Plan**

Statistical analyses include using appropriate categorical/continuous and parametric/non-parametric statistical test. Patient demographics (such age, gender, race ethnicity) and stone characteristics (such as stone volume, location, density) will be summarized as appropriate as continuous variables (mean and standard deviation) or categorical variables (frequency, percentage). To compare the two groups, procedural time, laser time, ablation speed, ablation efficiency, total energy used, are analyzed using Wilcoxon test. The score of quality of life survey and laser evaluation survey are analyzed using MANOVA. Complication rate is analyzed using chi-square. Statistical significance is set as two-tailed p value < 0.05 and data are analyzed using SPSS 25.

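### Stone-free rate, the first-listed secondary outcome, has only an unstratified chi-square in the protocol and no named analysis in the visible SAP, so its result will say little about whether time was saved at the cost of clearance

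*Protocol*

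**What the plan says.** The Project Summary makes clearance one of three headline comparisons: "Specifically, we will compare procedural time, intra-operative parameters and stone free rates". Research Design and Methods puts it first among the secondary outcomes: "1) stone free rate; (2) total operative time (minutes". The Study Objectives section also undertakes to compare primary and secondary outcomes by stone size, and Patient Randomization stratifies allocation by the two size bands (3-10 mm and 11-20 mm).

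For analysis, the protocol's Data Analysis section states "Categorical variables such as stone free rate will be analyzed using chi-square". The size-stratified method in that section (MANCOVA) is given for continuous variables only. The SAP's Data Analysis Plan names times, ablation measures, energy, two surveys and complications. Its only named categorical outcome is in "Complication rate is analyzed using chi-square". Its opening line allows for suitable categorical tests in general terms.

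Sample size rests on procedural time alone. The protocol states: "Group sample sizes of 33 and 33 achieve 80% power to detect a significant difference between the means". The inputs behind that figure are a 4.6-minute difference, an SD of 6.5 minutes and a two-sided t-test at 0.05. The allowance for losses raises 33 to 41 in each group, and 164 patients are planned in all. The visible text gives no expected stone-free rate, margin, confidence interval or power for clearance.

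**The concern.** Procedural time runs from scope insertion to removal, so stopping earlier shortens it. The stopping point is a fragment size judged by eye by a surgeon who knows which laser is in use. Postoperative stone-free status is the listed outcome that most directly shows whether a shorter procedure left more stone behind.

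The plan pairs a time comparison that is almost certain to detect its planned effect with a clearance test that has little power against a moderate loss. If the first is significant and the second is not, the p-value does not tell the reader how large a loss remains possible. An estimate with an interval would. The test as described also ignores the stratification used at randomization.

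**Working it through.** **1. The plan's own figure.** Inputs from Data Analysis: difference 4.6 min, SD 6.5 min, two-sided 0.05, 80% power.

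- Normal approximation: n = 2(1.96 + 0.842)² × (6.5/4.6)² = 2 × 7.85 × 1.997 = 31.3, so 32 per group.
- Noncentral t: n = 32.33, so 33 per group, with 80.8% power. The stated 33 reproduces.
- Inflation: 33 × 1.25 = 41.25, stated as 41. The total of 164 is 4 × 41, which implies 41 per laser in each size band and 82 per laser overall.

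**2. Power for time at 82 per laser.** SE = 6.5 × √(2/82) = 1.015. Then 4.6/1.015 − 1.96 = 2.57, so power is about 99%. The Wilcoxon test named in the SAP also gives about 99% under normality.

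**3. Power for stone-free rate at 82 per laser.** The rates are assumed. Power = Φ[(d − 1.96·s₀)/s₁], where s₀ = √(2p̄(1−p̄)/n) and s₁ = √((p₁(1−p₁) + p₂(1−p₂))/n).

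For 80% vs 70%: p̄ = 0.75, s₀ = 0.0676, s₁ = 0.0672. (0.10 − 0.1325)/0.0672 = −0.48, so power is 31% and the loss is non-significant 69% of the time. Exact enumeration of the chi-square test agrees; with Yates correction power falls to 26%.

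Chance that a true loss is non-significant, 82 per laser:

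| True loss | Better arm 60% | 70% | 80% | 90% | 95% |
|---|---|---|---|---|---|
| 5 points | 91% | 90% | 88% | 84% | 77% |
| 10 points | 75% | 73% | 69% | 57% | 43% |
| 15 points | 52% | 49% | 42% | 28% | 17% |
| 20 points | 27% | 25% | 20% | 10% | 5% |

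With 66 per laser evaluable (2 × 33), the 10-point row becomes 79/78/74/64/52%. Within one size band (41 per laser), power for a 10-point loss is 15/16/18/24/32%.

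**4. Both results together.** If the true time difference is the planned one and clearance is 80% vs 70%, the chance of a significant time result with a non-significant clearance result is at least 0.99 + 0.69 − 1 = 0.68, whatever the correlation between the two.

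**5. What an interval would show.** With equal observed rates, the 95% half-width is 1.96 × √(2p(1−p)/82): about 15, 14, 12, 9 and 7 points at 60, 70, 80, 90 and 95%. As an invented example, take 66/82 vs 57/82 stone-free. The difference is −11.0 points, z = 1.62, p = 0.10, and the 95% CI is about −24 to +2 points. The test says not significant; the interval shows that a 24-point loss is not excluded.

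**6. Ignoring the strata.** Suppose clearance is 95% in the small band and 65% in the large band (assumed).

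- Variance used by the unstratified test: 0.80 × 0.20 = 0.160.
- Average within-band variance: (0.0475 + 0.2275)/2 = 0.1375.
- The test's SE is therefore too large. Its effective cut-off is 1.96 × √(0.160/0.1375) = 2.11, a true type I error of about 3.4%.

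Simulation agrees: type I error about 3.4% unstratified against 4.9% stratified, and power about 30% against 36%, good to about one percentage point. If the bands have equal clearance, this gain disappears.

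**The case against.** Several points on the other side are sound.

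- **Reporting.** A reader might infer that a non-significant result will be published as no difference in clearance. Neither document says so. The plan simply supplies nothing that would let a reader judge otherwise.
- **Size of loss.** A reader might infer that any clearance loss would probably be missed. That fails for large losses: at 20 points power is 73 to 96% across the assumed rates, and at 15 points it is 72% and 83% when the better arm clears 90% and 95%. Even a 10-point loss has 57% power at 95%.
- **Omission.** A reader might infer that clearance has been dropped. The protocol does name it and its test, the SAP's general clause could cover it, and SAP text outside the Data Analysis Plan was not available here. The protocol likewise covers total operating-room time.
- **The test.** Chi-square is a valid test for a binary outcome, naming it does not forbid an estimate, and low power for a secondary outcome is ordinary. The trial states no non-inferiority aim for clearance. The by-size objective could be met by a test in each band, although the overall comparison would remain unstratified.
- **Common target.** Both arms are treated to small fragments of about 2 mm, which limits the scope for trading clearance for time. It does not remove it, because the size is estimated visually and unblinded.
- **Definition.** The visible text gives no definition of stone-free, and follow-up imaging may be x-ray or CT. An interval does not cure that.

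These points limit the claim. They do not supply an estimate, an interval or a stratified analysis.

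**Conclusion.** The point holds in a limited form. Stone-free rate has no named analysis in the visible SAP and only an unstratified chi-square in the protocol, in a trial sized on time alone and randomized within size bands. At 82 per laser, a 10-point loss would be non-significant about 57 to 75% of the time for better-arm rates of 60 to 90%, against about 99% power for the planned time difference. Losses near 20 points would usually be found.

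These figures assume the stated rates, all 164 patients evaluable and equal numbers per laser; losing patients makes them worse. The gain from stratifying depends on how far clearance differs between bands. The conclusion concerns how much the planned analysis can tell the reader. It is not evidence that either laser clears less stone, or that the sponsor will misreport the result.

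**What to change.** - Name stone-free rate in the SAP and state the definition and imaging on which it rests.
- Replace the chi-square with the thulium-minus-Moses difference in stone-free proportion and its 95% CI, Mantel-Haenszel pooled over the two randomized size bands. Each band's weight is n₁n₂/(n₁ + n₂), which is 20.5 in both bands at 41 per laser, so the estimate is then the average of the two band differences.
- Show the two by-band differences with their intervals. This meets the protocol's by-size objective for this outcome.
- Report the pooled difference beside the procedural-time result, and state that comparable clearance will not be claimed from p > 0.05.

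The cost is some SAP wording, a little more analysis and a table row or two, with no extra patients or imaging. The downside is that any claim of a faster laser becomes more guarded: at 80% clearance in both arms, the interval would still extend about 12 points either way.

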### **Data Analysis Plan**

Statistical analyses include using appropriate categorical/continuous and parametric/non-parametric statistical test. Patient demographics (such age, gender, race ethnicity) and stone characteristics (such as stone volume, location, density) will be summarized as appropriate as continuous variables (mean and standard deviation) or categorical variables (frequency, percentage). To compare the two groups, procedural time, laser time, ablation speed, ablation efficiency, total energy used, are analyzed using Wilcoxon test. The score of quality of life survey and laser evaluation survey are analyzed using MANOVA. Complication rate is analyzed using chi-square. Statistical significance is set as two-tailed p value < 0.05 and data are analyzed using SPSS 25.

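### The SAP's Wilcoxon test of procedural time names no stone-size stratum although randomisation is stratified by stone size, and neither document says which test decides the primary outcome

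*SAP*

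**What the plan says.** **Design.** The Protocol (Patient Randomization) allocates 1:1 in permuted blocks of four within two stone-size strata, 3–10 mm and 11–20 mm. Its reason, in Data Analysis, is "Previous literature suggested stone size is associated with operative time"; Study Objectives says much the same.

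**Protocol analysis.** Continuous outcomes, procedural time among them, "will be analyzed using T test and two-way MANCOVA (stratified by stone size 3 - 10 mm or 11-20 mm"). The next sentence adds "The surgeon will be controlled as a covariate". The sample size rests on an unadjusted comparison: "A significance level of 0.05 will be used with a two-sided two-sample equal-variance t-test", "when the mean difference is 4.6 minutes with a standard deviation of 6.5 minutes", and then "We also decide to increase the sample size by 25% (41 patients per group"), with 164 in total.

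**SAP analysis.** Procedural time is compared by Wilcoxon test ("procedural time, laser time, ablation speed, ablation efficiency, total energy used, are analyzed using Wilcoxon test"), two-tailed at 0.05. The SAP text available for review mentions neither stratum nor surgeon, and does not say whether the test is pooled or run within strata. The Protocol's secondary objective, comparison by stone size, does not appear in that text.

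**Stratum definition.** Data Analysis states "The stone size is defined as the largest stone size (largest diameter on pre-operative CT"), in line with the inclusion criteria. Study Procedures, step 5, groups patients by total stone size.

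**The concern.** The trial uses stone size to allocate patients because it expects size to affect how long the procedure takes. The SAP's named test of that time does not visibly use the same factor. Stratified allocation balances size between the arms, but an ordinary rank-sum test computes its variance as if that balance had been left to chance. If small and large stones take different times, the variance is too large, the true false-positive rate falls below 5%, and power is lost.

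The second gap is one of specification. A t-test, a stratified model and a Wilcoxon test all apply to the same primary outcome. Without a stated order, a reader cannot tell which p-value answers the primary question, and the choice could be made after the results are known.

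**Working it through.** **1. Reproduce the plan's sample size.** Inputs from Protocol, Data Analysis: difference 4.6 min, SD 6.5 min, two-sided 0.05, 80% power.

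- Normal approximation: n = 2 × (1.96 + 0.8416)² × (6.5/4.6)² = 2 × 7.849 × 1.9967 = 31.3, so 32 per group.
- Exact t-test power: 79.6% at 32 and 80.8% at 33. The plan's 33 is correct.
- 33 × 1.25 = 41.25, stated as 41, where power is 88.6%. Then 41 × 4 = 164, that is, two lasers by two strata. This suggests, without saying so, that each stratum was sized on its own.

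**2. The two statistics.** W is the rank sum of one arm with m of N patients.

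- Pooled Wilcoxon: z = [W − m(N+1)/2] / √[m(N−m)(N+1)/12].
- Van Elteren: rank within each stratum k, weight w_k = 1/(N_k+1), and z = Σ w_k[W_k − m_k(N_k+1)/2] / √Σ w_k² m_k(N_k−m_k)(N_k+1)/12.

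**3. Assumptions.** The documents give no gap in procedural time between strata and do not say whether 6.5 min is a within-stratum or an overall SD. Gaps of 0 to 15 min and both SD readings are therefore examined. The smaller effect, 2.85 min, is about what 164 patients detect with 80% power: (1.96 + 0.8416) × 6.5 × √(2/82) = 2.84, or 2.86 by the exact t-test.

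**4. Pooled reading, 6.5 min within stratum.** Simulation with blocks of four, 82 patients per stratum, normal times and 40,000 runs per setting (Monte Carlo SE at most 0.25 points):

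| Assumed gap (min) | 0 | 3 | 5 | 10 | 15 |
|---|---|---|---|---|---|
| True alpha, pooled (%) | 5.0 | 4.2 | 3.8 | 1.2 | 0.2 |
| Power at 4.6 min, pooled (%) | 99.2 | 99.2 | 98.9 | 96.7 | 89.7 |
| Power at 2.85 min, pooled (%) | 77.7 | 76.4 | 73.2 | 58.0 | 34.7 |

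Van Elteren over the same gaps: alpha 4.7–5.2%, power 99.2–99.3% at 4.6 min and 77.3–77.8% at 2.85 min. Separate simulations agree to about one point.

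- With 132 patients (4 × 33), pooled power at 4.6 min is 97.7/97.3/96.6/91.5/78.8%, against 97.3–97.7% stratified.
- With strata split 70:30, pooled power at 2.85 min is 74.1/62.0/45.4% at gaps of 5/10/15; with 85:15 it is 76.0/68.7/61.4%. Stratified power is 77.1–77.9%.

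**5. Pooled reading, 6.5 min overall.** Within-stratum SD = √(6.5² − (gap/2)²). Pooled power at 4.6 min is at least 99.3% with 164 patients and 97.5% with 132. At 2.85 min, gaps 0/3/5/10, it is 78.0/78.1/79.3/85.6%, against 77.7/79.4/83.7/98.9% stratified.

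**6. Within-strata reading.** Wilcoxon power in one stratum of 82 is 86.9% at 4.6 min and 47.9% at 2.85 min. If success in either stratum counts, the false-positive chance is 1 − 0.95² = 9.75%. If both must succeed, power at 4.6 min is 0.869² = 75.5%.

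**7. Which stratified test?** Power with 164 patients:

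| Assumed case | Pooled Wilcoxon | Van Elteren | Linear model with stratum |
|---|---|---|---|
| Normal, 2.85 min, gaps 0/5/10 | 77.7/73.2/58.0% | 77.2–77.6% | 79.6–79.9% |
| Lognormal shape (CV 0.5, SD 6.5), 2.85 min, gaps 0/5/10 | 91.7/85.5/66.5% | 91.5–91.9% | 79.7–80.0% |
| Effect 0.95 min (small stones) and 4.75 min (large), SDs 5.0 and 7.7, gaps 0/5/10 | 73.3/72.2/59.8% | 69.2–69.8% | 79.0–79.4% |

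In the last case van Elteren is 2–4 points below the pooled test at gaps of 0–5 min, 10 above it at 10 min and 33 above it at 15 min. With equal effects and no gap, stratifying costs at most about 0.5 points.

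**The case against.** The strongest reply is that the plan already has ample power. At its own 4.6 min the pooled test keeps 96.7% power at a 10-minute gap, and if 6.5 min is the overall SD nothing material is lost. The large losses need an effect or a gap that the documents do not give. This stands, and it limits the point to an improvement.

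It is also fair to say that the Protocol plans a size-stratified analysis that the SAP does not withdraw, that part of the SAP was not available for review, and that 41 × 4 = 164 fits per-stratum testing, under which there is no conservatism. All of this stands. It does not say which analysis is primary, and per-stratum testing brings its own missing rule.

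Four stronger readings should be resisted:

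- **That the unstratified test inflates false positives.** It does the opposite under stratified allocation.
- **That the SAP abandons stratification or the stone-size objective.** Silence in the text available does not show this.
- **That van Elteren is the only right choice.** The ranking against a stratum-adjusted linear model depends on a distribution that the documents do not describe: about 2 points worse with normal times, about 10 worse in the uneven case, about 12 better with the skewed times.
- **That stratifying is free in every case.** The uneven-effect case is a counterexample, and the Protocol's interest in large versus small stones makes an uneven effect conceivable.

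**Conclusion.** The point holds as a low-cost improvement and does not challenge the trial's validity. From the text alone, the SAP's test of the primary outcome names no stratum, the Protocol offers two further analyses, and no hierarchy is stated. Read as pooled, the test is valid and conservative to a degree set by the unknown gap between strata. At 4.6 min the cost is about 2.5 points of power at a 10-minute gap (99.2 − 96.7). At 2.85 min it is about 4 to 5 points at a 5-minute gap and 19 to 20 at 10 minutes. These figures assume normal times, equal strata, 164 analysed patients and 6.5 min as the within-stratum SD. If the strata do not differ, there is no loss. Read as within strata, what is missing is a decision rule. The case for a single stratum-aware primary test is firm; the choice between a rank test and a linear model is a judgement to be made before the data are seen.

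**What to change.** - Reconcile the Protocol's Data Analysis section with the SAP by naming one primary test of procedural time that uses the stone-size stratum assigned at randomisation. If the SAP's rank-based approach is kept, this is the van Elteren test, two-sided 0.05.
- Pre-specify a linear model for procedural time with laser, stratum and surgeon, as the Protocol intends, as the supporting estimate of the difference in minutes with a 95% CI. State that the two do not change places after the data are seen.
- Bring the stone-size objective into the SAP as per-stratum comparisons labelled secondary.
- Reconcile the total-size and largest-stone definitions, and state where the assigned stratum is recorded. The Protocol's confidentiality section says the enrollment log holds only participant ID and laser, so the randomisation list may be the source.

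The cost is a few sentences and a few lines of code. No extra patients or measurements are needed, provided the assigned stratum has been kept. The statistical price is the small or case-dependent loss shown above, which should be accepted knowingly when the test is chosen.
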